6.6. Continued Access to Study Intervention After the End of the Study

No intervention will be provided per protocol to study participants beyond the end of the study.

6.7. Treatment of Overdose

For this study, any dose of PF-07260437 greater than the intended dose level at any study intervention administration time point will be considered an overdose.

Sponsor does not recommend specific treatment for an overdose.

In the event of an overdose, the investigator/treating physician should:

1. Contact the medical monitor within 24 hours.

2. Closely monitor the participant for any AEs/SAEs and laboratory abnormalities for at least 5 half-lives or 28 calendar days after the overdose of PF-07260437 (whichever is longer).
3. Document the quantity of the excess dose as well as the duration of the overdose in the CRF.
4. Overdose is reportable to Pfizer Safety **only when associated with an SAE**.
5. Obtain a blood sample for PK analysis within 2 weeks from the date of the last dose of study intervention if requested by the medical monitor (determined on a case-by case-basis).

Decisions regarding dose interruptions or modifications will be made by the investigator in consultation with the medical monitor based on the clinical evaluation of the participant.

6.8. Concomitant Therapy

Concomitant treatment considered necessary for the participant's well-being may be given at discretion of the treating physician.

All concomitant treatments, blood products, as well as nondrug interventions (eg, paracentesis) received by participants from screening until the end of treatment visit will be recorded on the CRF.

Authorized or approved COVID-19 vaccines are considered allowed concomitant medications and standard AE collection and reporting processes should be followed. The timing of vaccine dosing relative to the dosing of study drug(s) is at the discretion of the investigator, although it may best to avoid the 7 days prior to C1D1 and the DLT observation period, to consider the potential for vaccine-related adverse events, and to administer the vaccine during scheduled dosing holidays, if applicable. Discussions between the investigator and the sponsor regarding individual cases may occur if further clarification is required.

PF-07260437 transiently increased serum cytokine levels (eg, IL-6) in monkeys *in vivo* and likely in patients (also demonstrated via *in vitro* human and monkey PBMC assays) which is expected with CD3-targeted bispecifics. Cytokines have been shown to result in down-regulation of some CYP450 enzymes. Therefore, treatment with PF-07260437 has a theoretical potential to increase the exposure of concomitant medications that are substrates for these enzymes. Caution should be used upon concomitant use of sensitive substrates of CYP450 enzymes with narrow therapeutic index (eg, CYP3A4: alfentanil, cyclosporine, dihydroergotamine, ergotamine, fentanyl, pimozide, quinidine, sirolimus and tacrolimus; CYP2C9: phenytoin, warfarin) especially during the initial treatment cycle. Refer to [Appendix 15](#) for details on the list of drugs which may result in a drug-drug interaction.

6.8.1. Prohibited and/or Limited use of Anti-tumor/Anti-Cancer or Experimental Drugs, or Procedures

No additional antitumor treatment will be permitted while participants are receiving study treatment.

In view of the current lack of data about the interaction of PF-07260437 with radiotherapy, palliative radiotherapy on study is permitted for the treatment of painful bony lesions provided that the lesions were known at the time of study entry and the investigator clearly indicates that the need for palliative radiotherapy is not indicative of disease progression. PF-07260437 treatment should be interrupted during palliative radiotherapy, stopping 7 days before and resuming treatment after recovery to baseline.

6.8.2. Supportive Care

Palliative and supportive care for disease related symptoms may be administered at the investigator's discretion and according to the specific supportive care product Prescribing Information or the current ASCO guidelines.

6.8.2.1. Supportive Care for Cytokine Release Syndrome

Symptoms associated with CRS vary greatly and may be difficult to distinguish from other conditions. The more common symptoms include fever, nausea, headache, tachycardia, hypotension, rash, and shortness of breath. The severity of symptoms can be mild to life threatening and thus there should be a high suspicion for CRS if these symptoms occur. The severity of CRS will be assessed according to the modified grading described by Lee et al ([Lee et al, 2019](#)). A suggested treatment algorithm for the management of CRS is also provided in [Appendix 11](#); however, if local standard of care is a different regimen this should be utilized.

The decision to incorporate pre-medication (ie, corticosteroids) for CRS prophylaxis in all participants will be made following discussions between the sponsor and the investigators. The pre-treatment medication will not be supplied by the sponsor.

6.8.2.2. Supportive Care for Immune Effector Cell-Associated Neurotoxicity Syndrome (ICANS)

ICANS is defined as disorder characterized by a pathologic process involving the central nervous system following any immune therapy that results in the activation or engagement of endogenous or infused T cells and/or other immune effector cells. Symptoms or signs can be progressive and may include aphasia, altered level of consciousness, impairment of cognitive skills, motor weakness, seizures, and cerebral edema. It has been observed following administration of some CAR T cells and bispecific antibodies and can occur independently of CRS. The severity of ICANS should be graded according to the ASTCT consensus criteria ([Lee et al, 2019](#)). General management guidelines can be found in Neelapu et al ([Neelapu et al, 2018; Neelapu, 2019](#)) or per local standard of care practice. These treatment guidelines may be modified as needed by the responsible investigator according to the best practices at their institute. Management guidelines are provided in [Appendix 11, Section 10.11.2](#).

6.8.2.3. Supportive Care for Infusion Related Reactions (IV infusion only)

IRR is characterized by fever and chills, and less commonly hypotension, either experienced by a particular participant or if seen in other participants, pretreatment medication should be administered to reduce the incidence and severity. In the event of IRRs, investigators should institute treatment measures according to best medical and nursing practice. A local standard of care for the management of IRR should be utilized.

6.8.2.4. Supportive Care for Injection Site Reactions (ISR)

ISR is a type of hypersensitivity reaction that may be immediate, although it usually appears within 24-48 hours after injection. ISR, by definition, includes the following erythema, pruritus, pain, inflammation, rash, induration, itching and edema at the injection site. To evaluate ISRs, site tolerability assessments will be performed per the [Schedule of Activities](#). ISR will not be considered DLTs but may be a reason for discontinuation of SC dosing.

Topical corticosteroids and topical or systemic antihistamines may be applied to treat any rash or pruritis at the injection site depending on the severity and per investigator's assessment.

6.8.2.5. Supportive Care for Hypersensitivity Reactions Types 1 and 3

Type 1 hypersensitivity or allergic (eg, shortness of breath, urticaria, anaphylaxis, angioedema) reactions are theoretically possible in response to any injected protein. Immune complex mediated Type 3 hypersensitivity reactions are similar to the AEs of Type 1 reactions but are likely to be delayed from the time of infusion and may include symptoms such as rash, urticaria, polyarthritis, myalgia, polysynovitis, fever, and, if severe, glomerulonephritis.

All participants should be closely observed while receiving study intervention and monitoring for clinical signs of a systemic reaction will continue thereafter for clinical signs of allergic reactions/hypersensitivity.

In the case of a hypersensitivity reaction, the participant will be treated symptomatically with supportive care, further monitoring, and treatment with antihistamines and/or corticosteroids. Study infusions may be stopped, and the participant will be followed until the end of the study.

Detailed guidance on treatment, dose interruptions and potential re-treatment is provided [Section 6.5](#).

6.8.2.6. Supportive Care for Immune-Related Adverse Events

For immunotherapeutic agents, treatment of irAEs is mainly dependent upon severity (NCI CTCAE grade version 5.0 (latest version as applicable). In general, Grade 1 or 2 irAEs are treated symptomatically with persistent Grade 2, Grade 3, or Grade 4 irAEs managed with moderate to high dose corticosteroids.

Guidelines on the treatment of irAEs are provided in [Appendix3, Section 10.3.5](#).

A more detailed summary of Management of Immune Related AEs is described in Brahmer et al ([Brahmer et al, 2018](#)).

6.8.3. Hematopoietic Growth Factors

Primary prophylactic use of colony stimulating factors is not permitted during the DLT assessment period in Part 1, but they may be used to treat treatment-emergent neutropenia as indicated by the current ASCO guidelines ([Smith et al, 2006](#)). During the screening window (ie, 14 days prior to Day 1), Granulocyte colony stimulating factors are not permitted to qualify a participant with low WBC counts.

Erythropoietin may be used at the investigator's discretion for the supportive treatment of anemia.

If the local indication and dosage of G-CSF compounds differs from ASCO guidelines, refer to the local product label or follow the country's clinical practice.

6.8.4. Antidiarrheal, Antiemetic Therapy

Primary prophylaxis is not recommended during the initial dose escalation. However, if the participant experiences nausea, vomiting or diarrhea, appropriate treatment and supportive care should be initiated. Prophylaxis may be considered for subsequent injections as well as for new participants at the investigator's discretion. The choice of the prophylactic drug as well as the duration of treatment is up to the investigator with sponsor approval assuming there is no known or expected drug-drug interaction and assuming the drug is not included [Section 6.8, Concomitant Therapy](#).

Diarrhea is a possible adverse event. As there is no prior clinical experience with PF-07260437, the exact nature of treatment related diarrhea in humans is unknown. In general, management of cancer treatment-induced diarrhea have been described ([Benson et al, 2004](#)). Initial management for mild to moderate diarrhea may include dietary modifications (eliminating lactose and other high-osmolar dietary supplements), loperamide or diphenoxylate/atropine, along with oral antibiotics if persistent with concern for infection. Management of higher severity or more complicated diarrhea may also include consideration of intravenous fluids for hydration, electrolyte replacement, octreotide, stool workup along with hospitalization for observation and treatment if indicated in the investigator's medical judgement. In addition, management of diarrhea as described in supportive care for irAEs for diarrhea ([Section 10.3.5](#)) may also be considered if the clinical impression of the etiology of diarrhea is associated with immune dysfunction

6.8.5. Corticosteroids

Chronic systemic corticosteroid use (prednisone >10 mg/day or equivalents) for palliative or supportive purposes is not permitted. Acute emergency administration, topical applications, inhaled sprays, eye drops, or local injections of corticosteroids are allowed.

6.8.6. Anti-Inflammatory Therapy

Anti-inflammatory or narcotic analgesic may be offered as needed assuming there is no known or expected drug-drug interaction and assuming the drug is not included [Section 6.8, Concomitant Therapy](#).

6.8.7. Surgery

Caution is advised for any surgical procedures during the study. The appropriate interval of time between surgery and PF-07260437 required to minimize the risk of impaired wound healing and bleeding has not been determined. Stopping PF-07260437 is recommended at least 7 days prior to surgery. Postoperatively, the decision to reinitiate PF-07260437 treatment should be based on a clinical assessment of satisfactory wound healing and recovery from surgery. Postoperatively, the decision to reinitiate PF-07260437 treatment should be based on a clinical assessment of satisfactory wound healing and recovery from surgery. Palliative radiotherapy to specific sites of disease will be permitted if considered medically necessary by the treating physician. All attempts will be made to rule out progressive disease in the event of increased localized pain.

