Part 2C: 2L+ participants with histological or cytological diagnosis of locally advanced or metastatic TNBC showing high B7-H4 expression (see [Section 8.6.2.1](#)) who have progressed after at least 1L of SOC chemotherapy and 1 line of SOC systemic therapy (eg, chemotherapy in combination with a checkpoint inhibitor if PD-L1 positive or chemotherapy alone if PD-L1 negative/low). De novo paired pre- and on-treatment biopsies are mandatory for approximately 5 participants.

4. Participants have at least 1 measurable lesion as defined by RECIST version 1.1 that has not been previously irradiated. For Part 1 dose escalation, participants with metastatic HR+ HER2- breast cancer with non-measurable but evaluable disease may be eligible after discussion with and approval from the sponsor.
5. Participants must be able to provide archival FFPE material containing tumor that is of diagnostic quality and representative of their diagnosed malignancy or consent to undergo a fresh biopsy during screening. 10 participants enrolling in Part 2B, and 5 participants enrolling in each of Parts 2A and 2C must agree to paired pre- and on-treatment biopsies. Ability of a participant to undergo biopsy safely should be determined during screening. Exceptions that biopsies cannot be obtained due to safety risk should be discussed and approved by the sponsor.
6. Participants with HR+ HER2- advanced or metastatic BrCa must have:
 - a. Documentation of ER or PR-positive tumor ($\geq 1\%$ positive stained cells) based on most recent tumor tissue utilizing an assay consistent with local standards and ASCO/CAP guidelines ([Allison et al, 2020](#))
 - b. Documentation that tumor is HER2-negative as determined by IHC score of 0/1+ or negative by *in situ* hybridization (FISH/CISH/SISH/DISH) defined as HER2/CEP17 ratio < 2 or for single probe assessment a HER2 copy number < 4 , consistent with ASCO/CAP guidelines ([Wolff et al, 2018](#)).
7. Participants with TNBC must have documentation that tumor tissue is negative ($< 1\%$ cells with nuclear positivity) for ER and PR as well as negative for HER2 as determined by IHC score of 0/1+ or negative by ISH (FISH/CISH/SISH/DISH) defined as a HER2/CEP17 ratio < 2 or for single probe assessment a HER2 copy number < 4 , consistent with ASCO/CAP guidelines ([Wolff et al, 2018; Allison et al, 2020](#)).

Informed Consent:

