10. Systemic anti-cancer therapy chemotherapy or endocrine therapy within 4 weeks or 5 half-lives (whichever is shorter) prior to first dose (6 weeks for mitomycin C or nitrosoureas). If the last immediate anticancer treatment contained an antibody-based agent(s) (approved or investigational), then an interval of 3 weeks or 5 half-lives (whichever is shorter) of the agent(s) prior to receiving the study intervention treatment is required.
11. Requirement for systemic immune suppressive medication [eg, ≥ 10 mg of prednisone or equivalent (≥ 1.5 mg of dexamethasone)]. Inhaled, intranasal, intraocular, intraarticular, and topical corticosteroids are allowed.
12. Major surgery within 3 weeks prior to first dose or during the study. Minor surgery may be allowed after consultation with and approval from sponsor.

13. Radiation therapy within 3 weeks prior to first dose or during the study. Palliative radiation to a limited field may be allowed after consultation with and approval from sponsor.

Blood product support:

14. Requirement for periodic blood product transfusions for a chronic condition. Blood product transfusions for transient and reversible cytopenias that are secondary to prior anti-cancer treatment are allowed after discussion with the sponsor.

Prior/Concurrent Clinical Study Experience:

15. Participation in other studies involving investigational drug(s) within 3 weeks or 5 half-lives (whichever is shorter) prior to first dose. A participant may be eligible even if they are in the follow-up phase of an investigational study as long as they haven't received treatment in the study for 4 weeks of 5 half-lives prior to first dose.

Diagnostic Assessments:

16. Serum or urine pregnancy test (for females of childbearing potential) positive at screening.
17. Participants with active, uncontrolled bacterial, fungal, or viral infection, including (but not limited to) HBV, HCV, COVID-19/SARS-CoV2, and known HIV or AIDS-related illness. Comments regarding specific circumstances follow:

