Disease sites must be assessed using the same technique as baseline, including consistent administration of contrast and timing of scanning. If a change needs to be made the case must be discussed with the radiologist to determine if substitution is possible. If not, subsequent objective statuses are indeterminate.

Target Disease

Complete Response (CR): Complete disappearance of all target lesions with the exception of nodal disease. All target nodes must decrease to normal size (short axis <10 mm). All target lesions must be assessed.

Partial Response (PR): Greater than or equal to 30% decrease under baseline of the sum of diameters of all target measurable lesions. The short diameter is used in the sum for target nodes, while the longest diameter is used in the sum for all other target lesions. All target lesions must be assessed.

Stable: Does not qualify for CR, PR, or Progression. All target lesions must be assessed. Stable can follow PR only in the rare case that the sum increases by less than 20% from the nadir, but enough that a previously documented 30% decrease no longer holds.

Objective Progression (PD): 20% increase in the sum of diameters of target measurable lesions above the smallest sum observed (over baseline if no decrease in the sum is observed during therapy), with a minimum absolute increase of 5 mm.

Indeterminate: Progression has not been documented, and

- one or more target measurable lesions have not been assessed;
- or assessment methods used were inconsistent with those used at baseline;
- or 1 or more target lesions cannot be measured accurately (eg, poorly visible unless due to being too small to measure);
- or 1 or more target lesions were excised or irradiated and have not reappeared or increased.

Non-target Disease

CR: Disappearance of all non-target lesions and normalization of tumor marker levels. All lymph nodes must be 'normal' in size (<10 mm short axis).

Non-CR/Non-PD: Persistence of any non-target lesions and/or tumor marker level above the normal limits.

PD: Unequivocal progression of pre-existing lesions. Generally, the overall tumor burden must increase sufficiently to merit discontinuation of therapy. In the presence of SD or PR in target disease, progression due to unequivocal increase in non-target disease should be rare.

Indeterminate: Progression has not been determined and 1 or more non-target sites were not assessed or assessment methods were inconsistent with those used at baseline.

New Lesions

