10.13. Appendix 13: Immune Related Response Criteria Derived from RECIST 1.1 (irRECIST)

Increasing clinical experience indicates that traditional response criteria may not be sufficient to fully characterize activity in this new era of targeted therapies and/or biologics.

The irRECIST tumor assessment system has been developed to incorporate delayed or flare type- responses into the RECIST v1.1 ([Nishino et al, 2014](#)).

For irRECIST, only target and measurable lesions are taken into account. In contrast to RECIST v1.1, irRECIST:

- Requires confirmation of both progression and response by imaging at least 4 weeks from the date first documented, and
- Does not necessarily score the appearance of new lesions as progressive disease if the sum of lesion diameters of target lesions (minimum of 10 mm longest diameter per non-nodal lesion and 15 mm shortest diameter per nodal lesion, maximum of 5 target lesions, maximum of 2 per organ) and measurable new lesions does not increase by ≥20%.

The same method of assessment and the same technique should be used to characterize each identified and reported target lesion(s) at baseline and throughout the trial.

irRECIST is defined as follows:

- Overall immune-related complete response (irCR): Complete disappearance of all lesions (whether measurable or not) and no new lesions. All measurable lymph nodes also must have a reduction in short axis to <10 mm.
- Overall immune-related partial response (irPR): Sum of the diameters (longest for non-nodal lesions, shortest for nodal lesions) of target and new measurable lesions decreases ≥30%.
- Overall immune-related stable disease (irSD): Sum of the diameters (longest for non-nodal lesions, shortest for nodal lesions) of target and new measurable lesions is neither irCR, irPR, (compared to baseline) or immune-related progressive disease (irPD, compared to nadir).
- Overall immune-related progressive disease (irPD): Sum of the diameters (longest for non-nodal lesions, shortest for nodal lesions) of target and new measurable lesions increases ≥20% (compared to nadir), confirmed by a repeat, consecutive observation at least 4 weeks from the date first documented.

New measurable lesions: Incorporated into tumor burden (ie, added to the target lesion measurements). A lymph node has to be ≥15 mm in short axis to be a measurable new lesion

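### Section 6.8.7 permits palliative radiotherapy at sites that Section 6.8.1 does not, and the irRECIST appendix does not say how an irradiated target lesion is scored

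*Protocol*

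**What the plan says.** Three places in the protocol bear on radiotherapy during treatment.

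- **Section 6.8.1** opens with a general bar: "No additional antitumor treatment will be permitted while participants are receiving study treatment". It then makes one exception: "palliative radiotherapy on study is permitted for the treatment of painful bony lesions provided that the lesions were known at the time of study entry". The investigator must also make clear that the need for radiotherapy is not a sign of progression. On dosing, "treatment should be interrupted during palliative radiotherapy, stopping 7 days before and resuming treatment after recovery to baseline".
- **Exclusion criterion 13 (Section 5.2)** covers radiation shortly before the first dose and also during the study. Its exception is: "Palliative radiation to a limited field may be allowed after consultation with and approval from sponsor".
- **Section 6.8.7**, under the heading Surgery, says: "Palliative radiotherapy to specific sites of disease will be permitted if considered medically necessary by the treating physician". Its last sentence asks that progressive disease be ruled out if localized pain increases.

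On scoring, Appendix 12 (RECIST 1.1) lists the cases in which target disease is indeterminate when progression has not been documented. One of them is "or 1 or more target lesions were excised or irradiated and have not reappeared or increased". Appendix 13 (irRECIST) says "For irRECIST, only target and measurable lesions are taken into account". It does not mention irradiation, and its Table 20 has no indeterminate or not-evaluable row.

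**The concern.** A site that reads 6.8.7 on its own has clear permission to irradiate a soft-tissue metastasis without contacting the sponsor. The same act is outside what 6.8.1 allows, and it lacks the approval that exclusion 13 requires. The protocol should not authorize in one subsection what it prohibits in another, least of all when 6.8.1 itself notes the lack of data on combining the drug with radiotherapy.

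The second consequence is for scoring. Inclusion criterion 4 asks for this minimum: "Participants have at least 1 measurable lesion as defined by RECIST version 1.1 that has not been previously irradiated". A participant may therefore have a single target lesion, and 6.8.7 allows it to be irradiated. RECIST 1.1 as written in Appendix 12 does not credit the resulting shrinkage to the drug. The irRECIST text contains no such statement, and responses are assessed by the investigator, so two sites could score the same scans differently.

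**Working it through.** **Step 1. The three provisions side by side**

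| | 6.8.1 | Exclusion 13 | 6.8.7 |
|---|---|---|---|
| Site | Painful bone lesion known at entry | Limited field | Any specific disease site |
| Who decides | Investigator, who indicates no progression | Sponsor approval | Treating physician |
| Drug hold | From 7 days before until recovery | Not mentioned | Not mentioned for radiotherapy (its 7-day stop concerns surgery) |
| Progression | Need must not indicate progression | Not mentioned | To be ruled out if local pain increases |

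The direct contradiction is in the first row, between 6.8.1 and 6.8.7. On approval, 6.8.7 omits what exclusion 13 requires. On the drug hold there is no contradiction: the 6.8.1 sentence applies to palliative radiotherapy generally, and 6.8.7 simply does not repeat it.

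**Step 2. Can a target lesion be reached?** Appendix 12 treats bone disease as non-measurable apart from measurable soft-tissue components. Radiotherapy under 6.8.1 will therefore seldom involve a target lesion. Radiotherapy under 6.8.7 can.

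**Step 3. When would Table 20, read literally, give irPR?** irPR needs a fall of at least 30% in the sum of target and new measurable diameters, confirmed at least 4 weeks later. Let s be the irradiated lesion's share of the baseline sum and x its proportional shrinkage, with the other lesions unchanged and no new ones. The condition is s × x ≥ 0.30. The shrinkage values are assumptions.

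- Single target (s = 1): 30% shrinkage is enough.
- Lesion halves (x = 0.5): s must be at least 0.30 / 0.50 = 60%.
- Lesion disappears (x = 1): s must be at least 0.30 / 1.00 = 30%.
- One of five equal lesions disappears: 0.20 × 1 = 20%, so no irPR.

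The gap matters mainly for participants with few target lesions or one dominant lesion.

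**Step 4. Size per participant.** The SAP's Response Evaluable set (Table 1) requires a dose, measurable baseline disease and a post-baseline assessment. An irradiated participant with those stays in the denominator. One move between irPR and not evaluable shifts irRECIST ORR by 1/20 = 5 percentage points in a cohort of 20. SAP Section 2.2 also summarizes response by disease type; in Part 2B, with about 10 participants per type, the shift is 1/10 = 10 points.

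Neither document gives the number likely to be irradiated, so no cohort-level shift can be calculated.

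**The case against.** The strongest reply is that the provisions can be read cumulatively. Section 6.8.1 is the section on prohibited and limited procedures, so it is the natural controlling text. Exclusion 13 is an eligibility criterion, and its approval condition can be met alongside either of the other rules. This stands in part: exclusion 13 adds a condition and does not contradict the others. It does not reconcile 6.8.1 with 6.8.7, which differ on the permitted site. No text tells the site to read them together.

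A reader might also infer that sites receive opposite instructions on holding the drug. The documents do not support that. The hold in 6.8.1 is general, and nothing in 6.8.7 tells a site to keep dosing.

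On scoring, the reply is that the Appendix 12 rule carries over. Appendix 13 is titled as derived from RECIST 1.1, irradiated lesions are not among the departures it lists, and SAP Section 6.2.4 calculates irRECIST response in a similar way to RECIST and provides a not-evaluable category. This is a plausible reading, so it would be too strong to say that irRECIST credits radiation shrinkage as response. The valid point is that the rule has to be inferred.

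Finally, RECIST 1.1 results are reported in parallel and are already protected, and a response confirmed before radiotherapy is unaffected. Both points stand and limit the consequence.

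**Conclusion.** The concern holds in a limited form. Section 6.8.7 contradicts 6.8.1 on which lesions may be irradiated and omits the sponsor approval in exclusion 13. Separately, Appendix 13 and Table 20 leave the scoring of an irradiated target lesion unstated.

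The effect is confined to irRECIST activity endpoints, which are secondary in Part 2 and exploratory in Part 1, with no hypothesis test. Its size is unknown. The 5-point figure is per affected participant, and the irPR thresholds assume Table 20 is applied literally with the shrinkage stated.

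A reader might go further and infer that the scoring gap hides progression, and that an indeterminate label would cure this, since treatment continues until irRECIST progression (Section 4.1). The second part does not follow. Take two 30 mm targets: the irradiated one halves to 15 mm and the other grows to 48 mm. The sum is 63 mm against 60 mm, or +5%, below the 20% needed for irPD. Under the Appendix 12 rule the status changes from irSD to indeterminate, but the sum still includes the irradiated lesion and irPD is still not reached. Earlier detection of progression is therefore not a benefit of the scoring change.

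**What to change.** **Conduct rule.** Delete the radiotherapy sentence from 6.8.7 and keep one rule in 6.8.1: painful bone lesions known at entry, progression ruled out, drug hold as now written. The 6.8.7 sentence on ruling out progression can move there. Allow any other site, or any target lesion, only after sponsor approval, in line with exclusion 13. Naming target lesions is an addition that none of the three texts now contains; it is what links the conduct rule to the scoring.

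**Scoring rule.** In Appendix 13, with a matching row in Table 20, state that irRECIST status is indeterminate when irPD has not been documented and a target lesion was irradiated and has neither come back nor grown, as in Appendix 12. The no-documented-progression condition must be kept, so that irPD from remaining or new lesions can still be called.

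**Cost.** Protocol wording only, with no new visits or data. A few irRECIST responses may become not evaluable, as they already would under RECIST 1.1. Palliation of soft-tissue disease would need a call to the sponsor but would not be banned.
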